2.4.1 Study Groups

1. Experimental Group 1 contained patients assigned with the numbers obtained after dividing the computer-generated random numbers by three, with a remainder of one.
2. Experimental Group 2 contained patients assigned with numbers obtained after dividing computer-generated random numbers by three, with a remainder of two.
3. The control group included patients assigned numbers obtained when the random numbers were divisible by three.

2.5 Intervention

Detailed history-taking, including medical history, and clinical exams were provided to all participants were, and written informed consent was obtained. A single-blind design was adopted, in which the participants did not know their inclusion status, or whether they were in the control or experimental groups. Double blinding was avoided due to ethical concerns and the questionable efficacy of the experiment. After obtaining informed consent from the patients, the project coordinators of each hospital opened the envelopes according to their serial number. They informed the catheterization nurse about the patient's inclusion status.

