2.5.2 Catheter Insertion Procedure

A fixed routine for pre-insertion cleaning and equipment was followed, including hand washing, placing the patient in the supine position, skin antisepsis, and preparation of the sterile field. Catheter insertion was performed by senior nurses in the intravenous treatment room, which was a standardized setting for venipuncture. Conventional catheter placement and maintenance methods were adopted as follows: ① evaluation: physicians confirmed the condition of the pre-puncture intima through ultrasound before catheterization. If ultrasound imaging did not show endothelium abnormalities, such as rough intima, it was noted as a smooth standard. Subsequently, 12 catheterization nurses selected the puncture site guided by ultrasound. Nurses took 1/3 of the middle part of the patient's upper arm as the best puncture area and used ultrasound to measure the diameter of the vessel (Chen et al., 2018). ② Catheterization: each hospital assigned two senior IV nurses for MC puncture and measured the catheter pre-placement length according to the measurement method of different groups, and the catheter was placed using ultrasound-guided and modified Seldinger techniques. After confirming the position of the tip, the catheter was trimmed, and the extension sets was connected, with the length of the external catheter were 3 cm. ③ Maintenance: 24 IV specialist nurses were trained to monitor and evaluate catheter functioning weekly, and clinical nurses conducted routine maintenance until study completion. Daily data were recorded and updated to computerized data records.

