2.6 Evaluation Indicators and Judgment Criteria

2.6.1 Incidence of Catheter-Related Complications

First, the catheter-related complications were assessed. The complications studied included phlebitis, catheter-related thrombosis, catheter occlusion, catheter dislodgement, bleeding, catheter-related infections, and infiltration. In this assessment, the incidence of each complication (i.e., number of patients with these complications) was divided by the total number of cases. Then, the total number of incidences of catheter-related complications was taken as the main outcome index (i.e., the number of patients with complications/the total number of patients). One patient with one or multiple complications was counted as one case in total.

The judgment criteria for each complication were as follows: ① phlebitis: the relevant contents in the Standard (Gorski et al., 2021) were considered; ② catheter-related thrombosis, also referred to as symptomatic thrombosis, was observed and reported either by patients or bedside nurses. Edema the limbs, neck, shoulder, chest, and/or face on the side of catheterization was observed for and reported to physicians, in order to perform an ultrasound for venous thrombosis detection; ③ catheter-related infections included local infection at the puncture site and catheter-related bloodstream infection, which were evaluated according to the corresponding diagnostic criteria in the Standard (Gorski et al., 2021); ④ catheter occlusion, inability to withdraw blood or sluggish blood return, sluggish flow; resistance or inability to flush lumen, inability to infuse fluid, Frequent occlusion alarms on electronic infusion pump. ⑤ catheter dislodgement included dislodgement of more than 3 cm; ⑥ infiltration was noted when the puncture site had liquid exudation; and ⑦ bleeding referred to the blood exudation at the puncture site 48 h after catheterization.

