2.7 Data Collection

Catheterization nurses recorded baseline data prior to catheterization, and only the most recent results were recorded one week prior to catheterization, when multiple laboratory results were available. Catheterization site evaluations were recorded after placement, and patients were followed up for 48 h after catheterization as well as every 7th day by IV specialist nurses to review and record the progress of antimicrobial therapy. The last follow-up was conducted at the time of removal, where the reason for removal was also recorded. In addition, bedside nurses evaluated and recorded catheter functioning and complications daily.

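### The plan provides for no blinding of the nurses who assess and record complications, so the partly subjective main outcome is open to differential recording between groups

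*Protocol*

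**What the plan says.** On blinding, Protocol 2.5 states: "A single-blind design was adopted, in which the participants did not know their inclusion status". It goes on: "Double blinding was avoided due to ethical concerns and the questionable efficacy of the experiment". The hospital coordinators opened the envelopes, and "They informed the catheterization nurse about the" patient's assignment. No other recipient is named, and no one is barred from learning it.

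On the outcome, Protocol 2.6.1 says that "the total number of incidences of catheter-related complications was taken as the main outcome index". A patient with any of seven complications counts once. For thrombosis, the symptomatic event "was observed and reported either by patients or bedside nurses", and that report leads to the ultrasound.

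On who assesses, Protocol 2.7 says that "bedside nurses evaluated and recorded catheter functioning and complications daily". IV specialist nurses visit at 48 h and every seventh day. Protocol 2.5.2 adds that "24 IV specialist nurses were trained to monitor and evaluate catheter functioning weekly".

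On what could reveal the group, Protocol 2.5.1 has the tip position checked by ultrasound during insertion and by X-ray afterwards. No limit on access to either result is described. The external part of the catheter gives less away: 2.5.2 describes one procedure "with the length of the external catheter were 3 cm", and 2.8 aims for a consistent external length from a single brand and batch.

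**The concern.** The inserting nurse has to know the target tip position. The people who decide whether a complication has occurred do not. The stated reason for going no further than participant blinding names no role and gives no specific ground for leaving assessors unblinded.

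This matters because of how the outcome is built. Sluggish flow or blood return, fluid or blood at the puncture site, and phlebitis are judged at the bedside. One borderline sign is enough to make a patient a case. Thrombosis is confirmed by ultrasound, but only in patients whose swelling was noticed and reported. The scan can remove false positives; it cannot recover patients who were never sent for one. Participant blinding protects only what patients themselves report.

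There is also a built-in expectation. The sample-size section (2.3) plans on 12.5% complications for subclavian tips and 32.5% for axillary chest-wall tips. A nurse who knows the tip position and shares that expectation could look harder, or call borderline signs more readily, in one group. That would bias the main comparison directly, and a larger sample would not cure it.

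**Working it through.** The plan gives no figure for this point, so there is none to reproduce. The check has three parts.

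**1. Is assessor blinding provided for anywhere?**

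| Place | Content | Keeps assessors unaware? |
|---|---|---|
| Protocol 2.5 | Participants blinded; double blinding avoided; inserting nurse told | No |
| Protocol 2.5.1 | Tip confirmed by ultrasound and X-ray | No access limit stated |
| Protocol 2.6.1 | Criteria for seven complications | No; common criteria only |
| Protocol 2.7 | Daily bedside recording; 48 h and weekly specialist visits | No |
| Protocol 2.8 | Training video, trained collectors, entry checks | No; consistency only |
| SAP | Tests and significance levels | No |

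**2. Could it be done with existing staff?** Twelve nurses insert (2.1), two per hospital (2.5.2), and 24 specialist nurses monitor (2.5.2). Overlap is not excluded. If all 12 inserters were among the 24, 24 − 12 = 12 monitors would still be non-inserters. An even spread would put 24 / 6 = 4 monitors in each hospital, but the spread is not stated. The bedside nurses who record daily are a separate group.

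**3. What could differential recording do?**

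Inputs:
- n = 110 per group (Protocol 2.4).
- Three-group chi-square test at two-sided 0.05 (SAP).
- Equal true rates p of 12.5% and 32.5% (the planning rates in 2.3) and their midpoint, 22.5%.
- Proportions of events recorded in control/Group 2/Group 1. These are assumptions; the documents give none.

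With recording proportion s, the recorded rate in a group is p × s. The test statistic is then approximately non-central chi-square on 2 degrees of freedom, with λ = n × Σ(pᵢ − p̄)² / [p̄(1 − p̄)].

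Worked case, p = 22.5% and 100/90/80%:
- Recorded rates are 22.5%, 20.25% and 18.0%, so p̄ = 20.25%.
- λ = 110 × (0.0225² + 0 + 0.0225²) / (0.2025 × 0.7975) = 0.111375 / 0.16149 = 0.69.
- The chance of exceeding the 5% critical value is about 10.6%. Simulation gives about 10.5%.

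False-positive rates by simulation:

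| Recording, control/Group 2/Group 1 | p = 12.5% | p = 22.5% | p = 32.5% |
|---|---|---|---|
| 100/100/100% | 5% | 5% | 5% |
| 100/95/90% | 5.5% | 6.2% | 7.1% |
| 100/90/80% | 7.4% | 10.5% | 14.4% |
| 100/85/70% | 11.2% | 18.9% | 28.5% |

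The spurious control-minus-Group 1 difference is p × (1 − s). It runs from 0.125 × 0.10 = 1.25 percentage points to 0.325 × 0.30 = 9.75 points.

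A pairwise check (normal approximation, one group under-recorded by 10%, 20% or 30%, the other fully recorded) gives false-positive rates from 2.2% to 21.9% at the SAP's pairwise level, against a nominal 1.7%.

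**The case against.** A reader might infer that the assessing nurses knew the allocation. The documents do not say so. The only disclosure described is from coordinator to inserting nurse, and the phrase about double blinding does not say which roles it covers. What is shown is a missing safeguard, not a known breach. Nor do the documents show that recording differed between groups.

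A reader might also infer that blinding was already in place in effect, because the catheters look alike. Equal external length supports feasibility, but the documents say nothing about dressings, labels or chart entries, and every patient has an X-ray showing the tip. Equal length alone does not settle the matter.

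The plan also has real mitigations. Protocol 2.8 provides a training video, assessment of bedside nurses, uniformly trained collectors and two layers of entry checks. Protocol 2.6.1 uses a published standard for phlebitis and infection, ultrasound for thrombosis and a 3 cm threshold for dislodgement. Blinded patients can report thrombosis symptoms themselves. These steps narrow the room for differing judgement, and components differ in how exposed they are. None of them stops an assessor who knows the group from applying a criterion unevenly, and entry checks cannot detect an event that was never recorded.

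Finally, spare monitoring nurses help only with the scheduled visits. The daily recorders are bedside nurses, so for them the protection must come from withholding the allocation and the tip report. The documents do not show how easily that would work on the wards. This objection stands, and it shapes the fix.

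**Conclusion.** The point holds as a gap in the plan: no blinding of outcome assessors is provided for, and nothing limits their access to the allocation or the tip result, while the main outcome is partly subjective. This is more than a missing detail, because the plan can be followed exactly and the main comparison still left exposed.

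The size cannot be known from the documents. Under the assumed gaps the false-positive rate ranges from about 5.5%, which is nearly harmless, to about 28.5%. That range rests on equal true rates, 110 analysed per group, and gaps applied to the whole composite in one direction. Reversing the direction gives the same rates with the sign of the spurious difference reversed. Equal under-recording in all groups would leave the rate at 5%.

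**What to change.** In Protocol 2.5, state that only the project coordinator, the inserting nurse and staff who need it clinically know the group. Then:

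- Keep the allocation and the X-ray and ultrasound tip report out of the ward observation table used by the daily bedside recorders until complication entries are locked.
- Have the 48 h and weekly assessments done by an existing monitoring nurse who did not insert that catheter.
- Leave the group off requests for thrombosis ultrasound.
- Log any unblinding for clinical reasons.

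The cost is protocol wording, a rota rule, separate filing of the tip report and a short log. The sample size does not change. The separate roles and uniform external length suggest that existing staff suffice, but each hospital should confirm that it has a non-inserting monitor.

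The Protocol describes conduct in the past tense. If assessors were in fact kept unaware, the sponsor should say so and describe how. If they were not, this should be stated as a limitation of the main outcome.

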2.5.1 Catheter Pre-Placement Length Measurement and Evaluation of Tip Position

The measurement of catheter pre-placement length and the determination method of catheter tip position were formulated based on the *Consensus* (Bai & Guo, 2019), expert opinions on vascular anatomy, and relevant literature (Huang et al., 2018; Pathak et al., 2015; Sun et al., 2014). An intravenous therapy (IV) specialist nurse confirmed catheter tip positioning by ultrasound during catheterization, and the position of the catheter tip was adjusted according to ultrasound imaging. X-ray imaging was performed after catheterization to confirm the position of the catheter tip. The measurement methods for the tip position and pre-placement insertion length of the different groups of catheters were as follows:

- (1) Experimental Group 1: The catheter tip was placed in the subclavian vein. The pre-placement catheter length measured through the body surface was greater than the actual length. Therefore, 2 cm was subtracted from the pre-puncture point to the ipsilateral sternoclavicular joint to calculate the effective catheter pre-placement length.
- (2) Experiment Group 2: The tip of the catheter was placed in the axillary vein of the chest wall. The pre-placement length of the catheter was measured by subtracting 3–4 cm from the distance between the puncture point and ipsilateral midclavicular line.

This adjustment was intended to prevent the catheter tip from entering the subclavian vein.

(3) The control group: the catheter tip was located distal to the axillary vein. The measurement method of catheter pre-placement length was as follows: in cases where the catheter was punctured from the basilic and brachial veins, the distance from the pre-puncture point to the intermuscular sulcus of the ipsilateral deltoid muscle and pectoralis major muscle was measured (not surpassing the intermuscular sulcus and not reaching the axilla); however, the distance from the pre-puncture point to the ipsilateral sub shoulder or axilla was measured.

2.5.2 Catheter Insertion Procedure

A fixed routine for pre-insertion cleaning and equipment was followed, including hand washing, placing the patient in the supine position, skin antisepsis, and preparation of the sterile field. Catheter insertion was performed by senior nurses in the intravenous treatment room, which was a standardized setting for venipuncture. Conventional catheter placement and maintenance methods were adopted as follows: ① evaluation: physicians confirmed the condition of the pre-puncture intima through ultrasound before catheterization. If ultrasound imaging did not show endothelium abnormalities, such as rough intima, it was noted as a smooth standard. Subsequently, 12 catheterization nurses selected the puncture site guided by ultrasound. Nurses took 1/3 of the middle part of the patient's upper arm as the best puncture area and used ultrasound to measure the diameter of the vessel (Chen et al., 2018). ② Catheterization: each hospital assigned two senior IV nurses for MC puncture and measured the catheter pre-placement length according to the measurement method of different groups, and the catheter was placed using ultrasound-guided and modified Seldinger techniques. After confirming the position of the tip, the catheter was trimmed, and the extension sets was connected, with the length of the external catheter were 3 cm. ③ Maintenance: 24 IV specialist nurses were trained to monitor and evaluate catheter functioning weekly, and clinical nurses conducted routine maintenance until study completion. Daily data were recorded and updated to computerized data records.

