2.2 Participants

A fixed-point continuous convenience sampling method was adopted to enroll 330 participants. The participants who met the clinical criteria for this study were informed about the study and written informed consent was obtained from each participant. Consent may also have been obtained from legally authorized persons. The inclusion criteria were as follows ① estimated time of intravenous infusion ≥ 1 week before catheterization; ② age: ≥ 18 years; ③ antimicrobial therapy was only used for treatment during hospitalization, with a pH value of 5–9 and osmotic pressure < 900 mOsm/L; and ④ patients were conscious and able to communicate normally. ⑤ The catheter-to-vessel ratio is less than 45%. The exclusion criteria were as follows: ① a history of radiotherapy, thrombosis, and trauma at the catheterization site and ② plans to discharge with a catheter during the study duration. Withdrawal criteria were as follows: ① active discharge from the hospital during indwelling of the catheter; ② failure to be followed-up after catheterization due to disease; and ③ a change in health status during antimicrobial therapy treatment, requiring other drugs to be infused treatment through the MC.

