2.4 Randomization and Grouping

There were 428 eligible patients, and 330 consented to participating in this study. A random sequence was generated after participants were recruited, and participants were randomized into three groups using a computerized random number generation

technique. Then, a proportional allocation of treatment methods was adopted to equalize the participants in all groups. Microsoft Excel generated 1000 random integers and 330 corresponding numbers were drawn. The 330 corresponding numbers were arranged into opaque and sequentially numbered envelopes. Then, the envelopes were sorted by random sequence and evenly distributed among the six selected hospitals. Three different study groups with equal numbers of participants (n=110) were established using this non-stratified random allocations.

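### The protocol does not require the vessel measurement behind the 45% inclusion limit, or the choice of vein and site, to come before the allocation is disclosed

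*Protocol*

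**What the plan says.** Protocol section 2.2, inclusion criterion 5: "The catheter-to-vessel ratio is less than 45" (per cent).

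Protocol section 2.4 gives the flow: "There were 428 eligible patients, and 330 consented to participating in this study". It adds: "A random sequence was generated after participants were recruited". The 330 are then allocated 110 to each of three groups.

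Protocol section 2.5 says that, after consent, "the project coordinators of each hospital opened the envelopes according to their serial number". It continues: "They informed the catheterization nurse about the patient's inclusion status". Only participants are blinded.

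Protocol section 2.5.2 has three steps. In the first (evaluation), a physician checks the vein lining by ultrasound; then "12 catheterization nurses selected the puncture site guided by ultrasound", and the nurses "used ultrasound to measure the diameter of the vessel". In the second (catheterization), the inserting nurses "measured the catheter pre-placement length according to the measurement method of different groups".

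Protocol section 2.5.3 lists site and vein among the data collected at catheterization, but neither vessel diameter nor the ratio. The SAP opens by describing an analysis that appears to be per protocol, and it names no intention-to-treat set.

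**The concern.** The ratio cannot be known until a vein and a site have been chosen and the vessel measured there. The person described as doing both is the nurse who inserts the catheter and who is told the content of the envelope. The trigger for opening the envelope is consent, not a completed vein assessment. The plan therefore contains no step that shields confirmation of this criterion, or the choice of vein and site, from knowledge of the group.

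Two things could go wrong. A patient found at or above the limit after disclosure might be excluded in one group more readily than in another. Or the nurse might choose a different vein or site according to the group, so that tip position is no longer the only systematic difference between groups. Vessel size plausibly bears on thrombosis, phlebitis and occlusion, which are components of the main outcome, so either route could bias the comparison. If the analysis is per protocol, patients excluded in this way could also leave the main analysis.

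**Working it through.** The point concerns the order of events and who knows what. There is no planned figure to reproduce, so the check sets the sections side by side.

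1. **What must be known for eligibility.** Section 2.2 requires the ratio, which needs the diameter of the vein to be used.
2. **Where the diameter is obtained.** Section 2.5.2, first step, is the only place in either document. Section 2.2 describes no screening measurement, and the physician's ultrasound in section 2.5.2 concerns the vein lining, with no diameter mentioned.
3. **What opens the envelope.** In section 2.5, consent does. The nurse is then informed. No time is given relative to the ultrasound.
4. **When the nurse must know the group.** By the second step of section 2.5.2, because the length measurement differs by group. Nothing in the first step needs the group, and nothing there says it is still concealed.
5. **What the flow implies.** In section 2.4, 428 were eligible, 330 consented and 3 × 110 = 330 were allocated. This implies that eligibility, including the ratio, was settled before consent. Steps 2 and 5 fit together only if a diameter was measured earlier, and none is described.
6. **What happens at 45% or above after allocation.** The three withdrawal criteria in section 2.2 do not cover it.
7. **Whether it could be audited.** With neither diameter nor ratio among the data in section 2.5.3, compliance with the criterion cannot be compared between groups.

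To give a sense of scale, suppose that one group only loses a fraction f of its patients, whose complication risk is k times that of the patients kept, and that the true rate is p in every group. The rate among those kept is r = p / [(1 − f) + f × k], and the bias is p − r. Take p = 22.5%, the midpoint of the two planning rates in section 2.3: (32.5% + 12.5%) / 2. The values of f (5% to 20%) and k (1.5 to 3) are assumptions; the documents give neither.

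- f = 0.05, k = 1.5: 0.225 / 1.025 = 21.95%; bias about 0.5 points.
- f = 0.10, k = 2: 0.225 / 1.10 = 20.45%; bias about 2.0 points.
- f = 0.20, k = 3: 0.225 / 1.40 = 16.07%; bias about 6.4 points.
- f = 0: bias zero.

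The planning difference in section 2.3 is 32.5% − 12.5% = 20 points. These figures illustrate selective exclusion only; they do not cover group-dependent vein choice.

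**The case against.** A reader might infer that the diameter was measured after the nurse had been told the group, and that patients at or above the limit were then dropped. The documents do not support that.

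- The order is not stated. It would have to be inferred from section 2.5 coming before section 2.5.2. Within section 2.5.2, the measurement precedes the first step that uses the group.
- What the nurse is told in section 2.5 is called inclusion status, which the same section mentions separately from group membership. The term is ambiguous.
- Section 2.4 suggests that eligibility was complete before consent, and its numbers show no loss between consent and allocation. The protocol describes no screening procedure for any criterion, so silence about an earlier diameter measurement does not show that there was none.
- Section 2.5.2 does not link its measurement to the 45% limit, and section 2.2 has no withdrawal rule for a ratio at or above it.
- Room for choice of site is limited: all groups share one preferred puncture area in the upper arm, and section 2.8 has one catheter brand and batch.

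All of this stands against the stronger reading. It does not remove the gap. No section requires the measurement and the choice of vein and site to precede disclosure. The nurse must know the group before the catheter is placed, and no other notification is described. The preferred area is a preference, and site and vein are recorded as items that vary. The total of 330 allocated says nothing about who was analysed or which vein was used. If section 2.4 is right about timing, the protocol still has to say where the ratio came from.

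**Conclusion.** The concern holds as a missing safeguard and an unreconciled account of timing. It is not evidence that selection took place. Sections 2.2, 2.4, 2.5 and 2.5.2 do not together say when the ratio was established relative to disclosure, and the stated trigger for the envelope leaves room for group-dependent exclusion or vein choice.

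The size of any bias cannot be estimated from the documents. It is zero if neither exclusion nor vein choice depended on the group. The range of about 0.5 to 6.4 points rests wholly on assumed values and on exclusions confined to one group; even its upper end is below the 20-point planning difference. The change is worth making because it closes a route to selection bias with a measurement the trial already takes. The conclusion assumes that the section 2.5.2 measurement, being the only one described, is the one that supplies the ratio. The remark about the analysis set assumes that the SAP means per protocol.

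**What to change.** Change the trigger in section 2.5: the envelope is opened only after the vein and puncture site have been chosen, the diameter measured, the ratio recorded and all inclusion criteria confirmed. Align sections 2.2, 2.4 and 2.5.2 with that order, and say plainly what the nurse is told and when. Add vessel diameter and ratio to the data listed in section 2.5.3. Report any post-allocation exclusions for the ratio by group. In the SAP, keep every randomized patient in the allocated group for the main analysis. This last item is a rule on the analysis set only and says nothing about catheter placement.

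The protocol is written in the past tense and gives a study period ending in January 2021. If enrolment is complete, the sponsor can still state the order actually followed, report exclusions by group and analyse all randomized patients as allocated.

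The cost is a small scheduling change, because the nurse's ultrasound must come before the envelope is opened, plus two further data items.
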